5.1.6 Management of Patients Who Experience Specific Adverse Events

5.1.6.1 Dose Modifications – Cohort 1

General dose modification guidelines for cobimetinib are provided in [Table 5](#). Dose modification guidelines for specific adverse events with combination treatment in this cohort are provided in [Appendix 12](#). Additional guidelines for the management of adverse events associated with atezolizumab are provided in [Appendix 14](#). After dose reduction, consideration may be given to allow for dose escalation of cobimetinib by a maximum of one dose level (20 mg) increments following resolution of the adverse event that resulted in dose modification to \leq Grade 1 and provided there are no safety concerns.

There will be no dose modifications for atezolizumab in this study.

Table 5 Recommended Cobimetinib Dose Modifications

Grade (NCI CTCAE)	Recommended Cobimetinib Dose
Grade 1 or Grade 2 (tolerable)	No dose reduction. Maintain cobimetinib at the same dose of 60 mg QD (3 tablets).
Grade 2 (intolerable) or Grade 3 or 4 (any)	
First appearance:	Interrupt treatment until Grade \leq 1: restart treatment at 40 mg QD (2 tablets).
Second appearance:	Interrupt treatment until Grade \leq 1: restart treatment at 20 mg QD (1 tablet).
Third appearance:	Consider permanent discontinuation.

NCI CTCAE = National Cancer Institute Common Terminology Criteria for Adverse Events;
QD = once a day.

5.1.6.2 Dose Modifications – Cohort 2

Run-in period (Cycle 1)

During the run-in period (Cycle 1, Days 1-28), one dose level reduction of cobimetinib and vemurafenib is permitted for management of drug-related toxicities. No further dose reductions are permitted in the run-in period. If toxicities do not improve within 28 days following the one level dose reduction and/or treatment interruption for either cobimetinib and/or vemurafenib, study treatment should be discontinued, unless *the patient is likely to derive clinical benefit. The decision to re-challenge patients with study treatment should be based on investigator's assessment of benefit–risk and documented by the investigator (or an appropriate delegate). The Medical Monitor is available to advise as needed.* The run-in period may be extended to a total of 56 days to allow patients to recover from drug-related toxicities prior to proceeding to Cycle 2. Following a dose reduction in the run-in period (Cycle 1), no escalation is permitted.

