- During the run-in period (Cycle 1), the dose of cobimetinib can be reduced by 20 mg QD (one dose level) from 60 mg daily to 40 mg daily during Days 1-21.
- If a vemurafenib dose reduction is required during Days 1-21, the dose of vemurafenib can be reduced from 960 mg BID to 720 mg BID. No further dose reductions of vemurafenib are allowed during Cycle 1.
- Drug-related toxicities presenting during the run-in period (Cycle 1) that require a vemurafenib dose reduction should be improving or have resolved (see [Appendix 13](#)) prior to Cycle 2, Day 1.

Patients must be receiving both study treatments in order to enter the triplet treatment period (Cycle 2, Day 1).

Triplet treatment period (Cycles \geq 2)

The dose of cobimetinib can be reduced by 20 mg QD (one dose level) decrements up to two times for management of drug-related toxicities (i.e. from 60 to 40 mg and then from 40 to 20 mg), except during the run-in period when only one dose reduction is allowed. If further dose reduction is indicated after two dose reductions, the patient must discontinue cobimetinib but may continue treatment with atezolizumab and/or vemurafenib at the investigator's discretion. The dose of cobimetinib may be escalated by a maximum of one dose level (20 mg) from 20 mg QD to 40 mg QD at the investigator's discretion in patients who have previously undergone dose reduction, provided there are no safety concerns and the adverse event that resulted in the dose reduction has resolved to \leq Grade 1. Dose escalation from 40 mg QD to 60 mg QD is not permitted.

There will be no dose modifications for atezolizumab in this study.

The dose of vemurafenib dose can be reduced during the triplet combination treatment period from 720 mg BID to 480 mg BID. If further dose reduction is indicated, the patient must discontinue vemurafenib but may continue treatment with atezolizumab and/or cobimetinib at the investigator's discretion.

Dose modification guidelines for specific adverse events with combination treatment in this cohort are provided in [Appendix 13](#) . Additional guidelines for the management of adverse events associated with atezolizumab are provided in [Appendix 14](#).

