6.1 DETERMINATION OF SAMPLE SIZE

The purpose of this Phase II study is estimation and hypothesis generation regarding the effect of cobimetinib plus atezolizumab on CNS metastases from BRAF^{V600} wild-type melanoma and the effect of cobimetinib plus atezolizumab and vemurafenib on CNS metastases from BRAF^{V600} mutation-positive melanoma. There are no reference data available on the use of these combination therapies in these patient populations.

There is no formal statistical hypothesis in this study. The originally planned total sample size of approximately 60 patients per cohort was based on an estimated study drop-out rate of 15%, the primary endpoint and 95% CIs for each treatment regimen. No power calculation has been performed.

In a Dear Investigator Letter dated 9 July 2019, the Sponsor communicated the decision to discontinue enrollment in the BRAF^{V600} wild-type cohort (Cohort 1). As of 9 July 2019, 15 patients were enrolled in Cohort 1. The 15 patients enrolled into the BRAF^{V600} wild-type cohort at the time of recruitment stop will be analysed descriptively only.

Point estimates and 95% CIs for a range of possible outcomes produced using nQuery (version 7) with 50 evaluable patients in the BRAF^{V600} mutation-positive cohort are provided in [Table 8](#) below.

Table 8 Objective Response Rate Estimates and Confidence Intervals with 50 Evaluable Patients per Treatment Cohort

Intracranial Response Rate in Cohort 2	95% Confidence Interval
35%	(21.8%, 48.2%)
40%	(26.4%, 53.6%)
45%	(31.2%, 58.8%)
50%	(36.1%, 63.9%)
55%	(41.2%, 68.8%)

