Table 11: QT Interval Prolongation

QT interval prolongation	
Event	Action to be taken
QTcF ≤ 500 ms with change from baseline in QTcF of < 60 ms	
 Continue all study treatment.
QTcF > 500 ms with change from baseline in QTcF of < 60 ms or QTcF ≤ 500 ms with change from baseline in QTcF of ≥ 60 ms	
 Withhold vemurafenib. Continue atezolizumab and cobimetinib. Rule out other risk factors for arrhythmia (e.g., myocardial ischemia). Check for electrolyte disturbances (e.g., potassium, magnesium and calcium). Evaluate concomitant medications to determine if there is co-administration of drugs that prolong QT interval. Refer patient to cardiologist. Monitor ECG weekly. If QTcF improves to ≤ 500 ms or baseline within 28 days, resume vemurafenib with dose reduced by one level. Repeat ECG at 2 and 4 weeks after resuming vemurafenib, on Day 15 of each subsequent cycle for three cycles, and then every 3 months thereafter. If QTcF does not improve to ≤ 500 ms or baseline within 28 days, permanently discontinue vemurafenib.
QTcF > 500 ms with change from baseline in QTcF of ≥ 60 ms	
 Permanently discontinue vemurafenib. Continue atezolizumab and cobimetinib. Rule out other risk factors for arrhythmia (e.g., myocardial ischemia). Check for electrolyte disturbances (e.g., potassium, magnesium and calcium). Evaluate concomitant medications to determine if there is co-administration of drugs that prolong QT interval. Refer patient to cardiologist. Monitor ECG weekly until QTcF improves to ≤ 500 ms or baseline.

ECG = electrocardiogram; QTcF = QT interval corrected using Fridericia's method.

Appendix 13: Guidelines for Management of Patients Who Experience Specific Adverse Events in Cohort 2

Table 12: Left Ventricular Ejection Fraction Decrease from Baseline

Left ventricular ejection fraction decrease from baseline				
Patient	LVEF Value	Recommended Action with Cobimetinib, Atezolizumab and Vemurafenib	LVEF Value following Treatment Break	Recommended Cobimetinib Daily Dose
Asymptomatic	≥ 50% or 40%–49% and < 10% absolute decrease from baseline	
 Continue all study treatment. 	Not Applicable	Not Applicable

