- Patients on a cobimetinib dose less than 60 mg will reduce by one dose level reduction (a 20-mg daily reduction), from a 40 mg daily dose to a 20 mg daily dose, and patients on a 20 mg daily dose at the time of the interruption (for LVEF decline) should discontinue cobimetinib.

Appendix 13: Guidelines for Management of Patients Who Experience Specific Adverse Events in Cohort 2

Table 13: Rhabdomyolysis or CPK Elevation

Rhabdomyolysis or CPK elevation	
Event	Action to be taken
General guidance	
 Consider withholding cobimetinib while investigating aetiology. Continue atezolizumab and vemurafenib. Assess patient for any history of strenuous physical activity, blunt trauma, or recent intramuscular injections. Evaluate for cardiac injury and rhabdomyolysis. If evidence of clinically significant cardiac injury or rhabdomyolysis, consider permanent discontinuation of cobimetinib.
Asymptomatic CPK elevation, Grade 1, 2, or 3	
 Continue all study treatment.
Rhabdomyolysis or symptomatic CPK elevation, Grade 1, 2, or 3	
 Withhold cobimetinib. Continue atezolizumab and vemurafenib. If event improves by at least one grade within 28 days, resume cobimetinib with dose reduced by one level. If not, permanently discontinue cobimetinib.
Rhabdomyolysis or CPK elevation (symptomatic or asymptomatic), Grade 4	
 Withhold cobimetinib. Continue atezolizumab and vemurafenib. If event improves to Grade \leq 3 within 28 days, resume cobimetinib with dose reduced by one level. If not, permanently discontinue cobimetinib.
Grade 3 or 4 or intolerable Grade 2 treatment-related toxicities not described above	
 Withhold all study treatment. If event resolves to Grade 1 or better within 12 weeks, resume atezolizumab at fixed dose. If not, permanently discontinue atezolizumab [a, b, c]. If event resolves to Grade 1 or better within 28 days, resume cobimetinib and vemurafenib with doses reduced by one level. If not, permanently discontinue cobimetinib and vemurafenib.

CPK = creatine phosphokinase.

- If corticosteroids have been initiated, they must be tapered over \geq 1 month to \leq 10 mg/day oral prednisone or equivalent before atezolizumab can be resumed.

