- Atezolizumab may be withheld for a period of time beyond 12 weeks to allow for corticosteroids to be reduced to \leq 10 mg/day oral prednisone or equivalent. The acceptable length of the extended period of time must be *based on an assessment of benefit–risk* by the investigator and *in alignment with the protocol requirements for the duration of treatment and documented by the investigator*. *The Medical Monitor is available to advise as needed*.
- Resumption of atezolizumab may be considered in patients who are deriving benefit and have fully recovered from the immune-mediated event. *The decision to re-challeng patients with atezolizumab should be based on investigator's assessment of benefit–risk and documented by the investigator (or an appropriate delegate)*. *The Medical Monitor is available to advise as needed*.

Appendix 13: Guidelines for Management of Patients Who Experience Specific Adverse Events in Cohort 2

Table 14: Haemorrhage

Haemorrhage	
Event	Action to be taken
Grade 3 events	
• Interrupt cobimetinib treatment. There is no data on the effectiveness of cobimetinib dose modifications for haemorrhage events.• Clinical judgment should be applied when considering restarting cobimetinib treatment.• Vemurafenib dosing can be continued when cobimetinib treatment is interrupted, if clinically indicated.• Continue atezolizumab treatment
Grade 4 events or cerebral haemorrhage (all grades)	
• Interrupt cobimetinib treatment.• Permanently discontinue cobimetinib for haemorrhage events attributed to cobimetinib.• Interrupt vemurafenib and restart if event improves within 28 days.• Continue atezolizumab unless clinically indicated.

Appendix 14

Risks Associated with Atezolizumab and Guidelines for Management of Adverse Events Associated with Atezolizumab

Toxicities associated or possibly associated with atezolizumab treatment should be managed according to standard medical practice. Additional tests, such as autoimmune serology or biopsies, should be used to evaluate for a possible immunogenic aetiology.

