## 5.6 SAFETY ANALYSES

Safety analyses will be performed on the safety evaluable population.

In addition, patients in Cohort 2 will receive cobimetinib and vemurafenib during the run-in period (Cycle 1) and the triplet combination (cobimetinib, atezolizumab and vemurafenib) from Cycle 2 onwards. For the purpose of safety analyses in Cohort 2, the patients will be grouped according to whether they have received the triplet combination:

- cobimetinib+vemurafenib (Patients who discontinued therapy prior to any atezolizumab administration): patients who received any amount of cobimetinib and/or vemurafenib without any amount of atezolizumab
- atezolizumab+cobimetinib+vemurafenib: patients who received any amount of atezolizumab in addition to cobimetinib+vemurafenib.

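### For Cohort 2 run-in toxicity, Protocol Section 5.1.6.2 and Appendix 13 conflict on how far an event must recover and what stops if it does not, and neither settles what follows when one targeted drug is lost

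*Protocol*

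**What the plan says.** **Protocol 5.1.6.2, run-in (Cycle 1).** One dose-level reduction of each targeted drug is allowed, and the run-in may last up to 56 days. The stopping rule begins "If toxicities do not improve within 28 days following the one level dose reduction and/or treatment interruption" and goes on "for either cobimetinib and/or vemurafenib, study treatment should be discontinued, unless", the exception being a patient likely to benefit. Section 4.3 defines study treatment as the cohort's combination. A toxicity that needed a vemurafenib reduction should be resolved, or on the way there, before Cycle 2 Day 1; this bullet points to Appendix 13. Entry to the triplet period is conditional: "Patients must be receiving both study treatments in order to enter the triplet treatment period (Cycle 2, Day 1".

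**Protocol 5.1.6.3.** A targeted drug withheld for more than 28 days is itself stopped, with the same benefit exception. Run-in interruptions are referred to 5.1.6.2.

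**Protocol Appendix 13.**
- Table 1 repeats the general rule that only the drug withheld for more than 28 days is stopped, and limits it to no period.
- Table 5 has rows labelled for the run-in. Grade 3 elevations of ALT, AST or bilirubin, and a first Grade 4 episode, must reach Grade 1 or better within 28 days. Otherwise the patient leaves the study.
- Table 4 (Grade 3 non-acneiform rash) and Table 13 (symptomatic CPK elevation or rhabdomyolysis) name no period. If recovery fails at 28 days, each stops one targeted drug and continues the rest.
- Table 11 names no period. For QTcF above 500 ms with a change of at least 60 ms it says "Permanently discontinue vemurafenib. Continue atezolizumab and cobimetinib".
- The residual row at the end of Table 13, also without a period, asks for Grade 1 or better within 28 days: "resume cobimetinib and vemurafenib with doses reduced by one level. If not, permanently discontinue cobimetinib and vemurafenib".

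**The concern.** A site with a toxic run-in patient has two sets of instructions that do not agree. Three points are open: how much recovery is enough, whether one drug or all treatment or study participation ends, and what becomes of a patient who can no longer take one of the two targeted drugs.

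The first stake is safety, because these rules govern the step at which atezolizumab is added. The second is the analysis. Protocol 4.5.6 keeps scanning patients who stop treatment without progression, but a patient taken off the study is no longer scanned. The Evaluable population, used for the primary intracranial ORR, needs two post-baseline intracranial assessments (SAP Section 4). The page a site follows can therefore decide whether an early-toxicity patient can be in the primary denominator.

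**Working it through.** The point disputes no power or sample-size figure; the protocol says "There is no formal statistical hypothesis in this study". The check is to take one run-in patient at a time through both sets of rules.

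| Run-in patient | Section 5.1.6.2 | Appendix 13 |
|---|---|---|
| A. Grade 3 ALT, down to Grade 2 at day 28 | Improved, so the stopping rule is not triggered | Table 5 run-in row: not Grade 1, so off study; no benefit exception in the row |
| B. Grade 3 non-acneiform rash, not improved at day 28 | All study treatment stops unless benefit is likely | Table 4: vemurafenib stops; cobimetinib and atezolizumab continue |
| C. QTcF above 500 ms with a change of at least 60 ms at the Cycle 1 Day 15 ECG, later improved | Cycle 2 barred without both drugs; nothing says whether cobimetinib alone goes on | Table 11: vemurafenib stops for good; the rest continues |

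**Case A** is the firmest, because the liver rows are explicitly labelled for the run-in. **Case B** runs the other way: here 5.1.6.2 stops more than Appendix 13 does. **Case C** is a gap in 5.1.6.2. It is foreseeable, since Appendix 2 schedules an ECG on Day 15 of Cycle 1. Table 14 can raise the same question: "Permanently discontinue cobimetinib for haemorrhage events attributed to cobimetinib", with vemurafenib restarted if the event improves within 28 days.

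**Is the 56-day limit a further conflict?** A 28-day window opening on run-in day d closes on day d + 28:
- d = 1 gives day 29
- d = 15 gives day 43
- d = 21 gives day 49
- d = 28 gives day 56

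All fall within 56 days, so it is not.

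**Effect on the Evaluable population.** Without delays, Cycle 1 is days 1–28 and Cycle 2 is days 29–56, so the first scheduled scan, in the last week of Cycle 2, falls on days 50–56. A patient taken off study when a window opened on or before day 21 closes leaves by day 49, before any scheduled scan. A window opened on days 22–28 closes within the scan week, so at most one scheduled scan is possible; the next is due about 8 weeks later. Either way the patient lacks two scheduled assessments. Under a reading that stops treatment only, scanning continues and both can be obtained.

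**Size.**
- The documents give no rate for these situations. The nearest figure, in Protocol 5.1.1.7, is 20.5% with Grade 3 or higher liver laboratory adverse events on cobimetinib plus vemurafenib in the Phase III study. 0.205 × 60 = 12.3, about 12 patients. That figure is not limited to the run-in and does not count patients who improve without reaching Grade 1, so it is upper context, not an estimate.
- To illustrate the effect on ORR, suppose 25 of 50 evaluable patients respond (50%). Adding one non-responder gives 25/51 = 49.0%, a shift of about one percentage point per patient. The planned interval at 50% is 36.1% to 63.9%.

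**The case against.** The best defence is that the documents set an order of precedence and leave room for judgement. Section 5.1.6.3 and Appendix 13 Table 1 send run-in interruptions and reductions to 5.1.6.2. The bullet on recovery before Cycle 2 points to Appendix 13, so it may defer to the event rows. The 28-day sentence is a trigger for stopping, not a permission to proceed, so a site could satisfy both texts by applying the stricter. Section 5.1.6.5 says the guidelines do not replace clinical judgement, and it exempts reversible laboratory abnormalities without clinical significance.

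Some of this stands. The exemption will remove some liver cases, and a stricter-rule reading would settle case A. But the pointers run in a circle: interruptions go to 5.1.6.2, and the recovery test goes back to Appendix 13. Nor does applying the stricter page serve as a general rule. In case A it overrides the benefit exception, and in case B it contradicts the row's instruction to continue the other drugs. A general appeal to judgement does not choose between a mandatory entry condition and a row that points elsewhere.

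Several stronger readings are tempting, and the documents do not support them:
- **That Appendix 13 tells sites to start atezolizumab after one drug is lost.** An instruction to continue presupposes that atezolizumab has begun. Section 4.3.2.2 withholds it in the run-in, and the entry rule is mandatory.
- **That a single-drug patient falls outside both SAP 5.6 safety groups.** One group is "patients who received any amount of atezolizumab in addition to cobimetinib+vemurafenib". The operative definition of the other covers any cobimetinib, vemurafenib or both without atezolizumab, which includes this patient; only its parenthetical label fits badly.
- **That only the liver table separates the periods.** Appendix 13 Table 1 also does so for dose changes.
- **That Appendix 13 always demands Grade 1.** The Grade 3 rash rows use Grade 2, and the CPK rows use a one-grade improvement or Grade 3 or lower.
- **That cobimetinib toxicities have no recovery rule.** The 28-day sentence covers either drug.

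**Conclusion.** The protocol is wrong as written: an internal inconsistency that should be corrected. Three elements hold.

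1. Section 5.1.6.2 asks for improvement, while the labelled run-in liver rows ask for Grade 1 or better or removal from the study.
2. When recovery fails at 28 days, 5.1.6.2 stops the combination, while Appendix 13's general rule and several rows stop one drug.
3. Section 5.1.6.2 gives no outcome for a run-in patient who permanently loses one targeted drug but whose event improves.

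The first element needs no assumption about scope. In the second, the conflict with individual rows, and in the third, the loss of a drug under a row such as Table 11, assume that rows without a stated period apply in Cycle 1. Nothing in those rows excludes it, though Table 1 gives some reason for caution.

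The number of patients affected cannot be derived from the documents. The main consequence is safety at the addition of the third drug. The statistical consequence is narrower: membership of the Evaluable population. The SAP repeats the primary analysis (5.3.3), and unless otherwise noted the secondary efficacy analyses (5.4), in all treated patients. A reader might infer that the Cohort 2 ORR and PFS become uninterpretable, but neither efficacy set requires atezolizumab, and the all-treated set is the same under every reading.

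**What to change.** Reconcile Sections 5.1.6.2 and 5.1.6.3 with Appendix 13 Tables 1, 4, 5, 11 and 13:

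- State one recovery criterion for leaving the run-in, or say that the event-specific row governs, and whether the benefit exception applies to it.
- For toxicity that has not recovered, state whether one drug, all study treatment or study participation ends.
- State what applies when one targeted drug is permanently stopped in Cycle 1.
- Mark in each Appendix 13 table which rows apply in Cycle 1.

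Which clinical rule is adopted is for the sponsor's clinical team; the statistical need is only that there be one. The cost is protocol wording. No extra data, patients or change to the SAP safety groups is required.
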